The sponsor will appoint a DSMB consisting of an independent group of clinical experts, who are not participating in the study. They will be supplemented by an independent statistician. The objective of the DSMB will be to review unblinded safety data on SAEs with a focus on mortality rate. Acquired TTP is still associated with a mortality rate of 10 – 20% and an efficacious treatment may reduce this. The first DSMB meeting will be convened as of 5 deaths, or after 24 subjects have completed the study drug treatment period, whichever occurs earlier. This is to review the SAE and mortality information (including the overall number of subjects treated up to that point, rates, and subject-level details) and determine if there is an imbalance in the treatment arms with respect to these events, based on clinical judgment of the DSMB. Subsequent meetings will be determined by the DSMB based on the recruitment rate into the study, and incidence of SAEs, particularly death. The DSMB will advise the sponsor concerning continuation, modification or termination of the study after every meeting.

The composition, objectives, and role and responsibilities of the independent DSMB will be described in a DSMB charter, agreed with the DSMB members and Sponsor. The DSMB charter will also define and document the content of the safety summaries, and general procedures (including communications).

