3.5.2. SERIOUS ADVERSE EVENTS

An SAE is any untoward medical occurrence that at any dose meets any of the following conditions:

- Results in death.

- Is life-threatening: the subject is at risk of death at the time of the event. It does not refer to an event that hypothetically might cause death if it were more severe.
- Requires in-patient hospitalization or prolongation of existing hospitalization; an AE associated with a hospitalization or prolongation of hospitalization will not be regarded as an SAE if at least one of the following exceptions is met:
 - The admission results in a hospital stay of less than 12 hours.
 - The admission is pre-planned (i.e., elective or scheduled surgery arranged prior to the start of the study).
 - The admission is not associated with an AE (e.g., social hospitalization for purposes of respite care).

However, it should be noted that invasive treatment during any hospitalization may fulfill the criterion of "medically important" and as such may be reportable as an SAE dependent on clinical judgment. In addition, where local regulatory authorities specifically require a more stringent definition, the local regulation takes precedence.

- Results in persistent or significant disability/incapacity. Disability means a substantial disruption of a person's ability to conduct normal life's functions.
- Results in a congenital anomaly/birth defect.
- Is another medically important serious event as judged by the Investigator, or is defined as requiring intervention to prevent one of the outcomes listed in the definition above (including suspected transmission of an infectious agent by a medicinal product should be reported as an SAE). Other examples of such events are intensive treatment in an emergency room or at home for allergic bronchospasm; blood dyscrasias or convulsions that do not result in hospitalization; or development of drug dependency or drug abuse. Any AE is considered an SAE if it is associated with clinical signs or symptoms judged by the Investigator to have a significant clinical impact.

All exacerbations and relapses must be considered covered by the "another medically important serious event" criterion and must be reported as SAE.

A treatment-emergent SAE is any SAE temporally associated with the use of study drug, whether considered related to the study drug or not.

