3.3.2 Secondary endpoints

3.3.2.1 Key secondary endpoints

The key secondary endpoints are hierarchically ordered as listed below:

1. Proportion of subjects with TTP-related death, a recurrence of TTP, or at least one treatment-emergent major thromboembolic event during the study drug treatment period (including extensions).
2. Proportion of subjects with a recurrence of TTP in the overall study period (including the 4-week follow-up [FU] period).
3. Proportion of subjects with refractory TTP, defined as absence of platelet count doubling after 4 days of standard treatment, and LDH $>$ upper limit of normal range (ULN).

CONFIDENTIAL

4. Time to normalization of all 3 of the following organ damage marker levels: LDH, cTnI, serum creatinine.

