Exacerbations and relapses will be documented as serious adverse events. Note that, exceptionally, daily PE may have been stopped before an initial platelet count $\geq 150 \times 10^9/L$ is reached, by investigator's decision. It is recognized that in this case the subject can still experience an exacerbation or relapse requiring re-initiation of daily PE if documented as described above.

- Treatment-emergent major thromboembolic event: e.g., myocardial infarction, cerebrovascular accident, pulmonary embolism or DVT, confirmed after adjudication (see below).

If a potential major thromboembolic event or TTP-related death occurs, the investigator will be requested to provide additional information for adjudication by a blinded independent committee. Only events that are confirmed after adjudication will be used for the analysis. More details are provided in CSP Section 3.4.3.6 and [Appendix B: Adjudication charter](#).

2. Proportion of subjects with a recurrence of TTP in the overall study period (including the FU period). A CMH test will be conducted with adjustment for GCS category (stratification factor used in randomization). For both treatment groups, only recurrences that have occurred prior to a potential switch to open-label caplacizumab will be evaluated for this analysis.
3. Proportion of subjects with refractory TTP, defined as absence of platelet count doubling after 4 days of standard treatment, and LDH $>$ ULN. A CMH test will be conducted with adjustment for GCS category (stratification factor used in randomization). Refractory TTP is derived as follows: (platelet count after 4 days of standard treatment / platelet count at start of standard treatment) $<$ 2 and LDH $>$ ULN after 4 days of standard treatment. Platelet count and LDH at Day 5 will be used for this analysis. Subjects who have reached platelet count response (primary endpoint) by Day 5 will not be considered as having a refractory TTP.

Subjects discontinued (lost to follow-up, withdrew consent, etc...) before day 5 will be excluded from the analysis.

CONFIDENTIAL

Missing values will be imputed using multiple imputation (Markov Chain Monte Carlo) by averaged simulated parameter values. The number of simulation iterations will be adapted to the proportion of missing values (0-10% missing values: 20 iterations, 10-20% missing values: 100 iterations) to keep the relative efficiency (RE) of multiple imputation under control (Rubin, 1987).

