7.1 Adverse Events

7.1.1 Methods and definitions

All adverse events will be coded using the latest version of the Medical Dictionary for Regulatory Activities (MedDRA).

All adverse events starting or worsening in severity (for pre-existing conditions) from the start of study drug administration until completion of the subject's last visit are considered treatment-emergent adverse events (TEAE).

Adverse events will be placed into analysis periods (phases, periods and subperiods) according to their start date(time). The AE will only be presented in the analysis period during which it started, i.e. period start date(time) \leq AE start date(time) \leq period stop date(time). There will be no imputation of other missing date(time) fields, nor of the missing parts of other partially known date(time) fields. When needed (e.g., an incomplete date(time) leads to a double phase allocation), the following rules will be applied: adverse events will be allocated on all analysis levels (i.e., for analysis phases, periods and subperiods, see Section 4.4) according to their start date(time). In case the adverse event (AE) start date(time) is incomplete, the allocation will be done according to the available parts of the AE start date(time) and taking into account the AE end date(time) (i.e., the AE start date(time) cannot be later than the AE end date(time)):

- When, due to missing date(part) an allocation needs to be made to an analysis phase, the AE will be allocated to the treatment phase and not the screening or follow-up phase (worst-case allocation).
- When an allocation needs to be made within the treatment phase to an analysis period, the AE will be allocated to the double-blind treatment period.
- When an allocation needs to be made within an analysis period, the event will be allocated to the daily PE subperiod.

CONFIDENTIAL

If the AE start date is completely missing but AE end date and study drug administration are non-missing and AE end date is before the first study drug administration and after signing ICF, then the AE is defined as pre-treatment. All adverse events emerging during the screening period will only be listed and will not be presented in any of the tables. These events are not TEAEs. All tables will thus present TEAEs only.

According to ICH-E3, the drug relatedness as assessed by the investigator will be dichotomized as follows:

- Drug-related: at least possibly drug-related, OR with a missing drug-relatedness (= worst-case).

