7.1.2 Analysis

The following analysis periods will be considered for all AE tables:

- DB treatment daily PE period
- DB treatment post-daily PE period
- OL treatment daily PE period
- OL treatment post-daily PE period
- Overall treatment period
- FU period
- Overall study period

Summaries on AEs will be presented by treatment group (Caplacizumab, Placebo, OL Caplacizumab, Caplacizumab Total) and by analysis period. The 'Caplacizumab Total' group will combine events that have occurred for all caplacizumab-treated subjects. For subjects who received placebo in the DB treatment period, only events after switch to open-label caplacizumab will be counted for the Caplacizumab Total group.

A general summary table will be presented by treatment group and analysis period, reporting the number and percentage of subjects, the number of events and the incidence per 100 patient months, which will be calculated as: $100 \times (\text{Number of subjects with AE}) / (\text{Total number of months observed within analysis period, summed for all subjects})$. The following categories will be included in the summary table:

- Subjects with at least one TEAE
- Subjects with at least one serious TEAE
- Subjects with at least one TEAE leading to death
- Subjects with at least one TEAE for which the study drug was interrupted
- Subjects with at least one TEAE for which the study drug was withdrawn
- Subjects with at least one TEAE that was considered at least possibly treatment-related by the investigator
- Subjects with at least one serious TEAE that was considered at least possibly treatment-related by the investigator
- Subjects with at least one bleeding event, i.e. an event documented as event indicating an increased bleeding tendency
- Subject with at least one bleeding event, based on the Standardized MedDRA Query (SMQ) 'Haemorrhage terms (excluding laboratory terms)'
- Subjects with at least one thromboembolic event, based on the SMQ 'Embolic and thrombotic events (arterial, venous, and vessel type unspecified and mixed arterial and venous)'
- Subjects with at least one hypersensitivity reaction, based on the SMQs 'Hypersensitivity' (Narrow), 'Anaphylactic reaction' (Narrow) and 'Angioedema' (Narrow)
- Subjects with at least one hypersensitivity reaction, based on the SMQs 'Hypersensitivity' (Narrow), 'Anaphylactic reaction' (Narrow) and 'Angioedema' (Narrow), considered at least possibly treatment-related by the investigator.

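### The headline serious-TEAE row counts every TTP recurrence, an efficacy outcome, and no readable row counts subjects with any other serious event

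*SAP*

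**What the plan says.** Protocol 3.5.2 places all exacerbations and relapses under the medically important event "criterion and must be reported as SAE", and Protocol 3.4.8.1 says the same. SAP 6.2.1 repeats it: "Exacerbations and relapses will be documented as serious adverse events".

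Under SAP 7.1.1 an event is treatment-emergent if it starts or worsens between first dose and last visit, and it is assigned to a period by its start date. Where an incomplete date leaves the period within the treatment phase open, "the AE will be allocated to the double-blind treatment period". SAP 4.4.1 starts the open-label period at the first open-label dose.

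Table 14.3.1.1 reports, by treatment group and analysis period, the number and percentage of subjects, the number of events and the incidence per 100 patient-months. One row is "Subjects with at least one serious TEAE". Neither SAP 7.1.2 nor the table index in SAP 14.6 excludes TTP recurrence from it.

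The first two key secondary endpoints in SAP 3.3.2.1 are "Proportion of subjects with TTP-related death, a recurrence of TTP, or at least one treatment-emergent major thromboembolic event" during study drug treatment, and "Proportion of subjects with a recurrence of TTP in the overall study period".

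**The concern.** A recurrence that triggers the switch begins before the first open-label dose, so it is counted as a serious TEAE in the randomized arm's column. The row therefore adds an outcome the drug is meant to prevent to the serious events it might cause. If caplacizumab reduces on-treatment recurrence, the placebo percentage rises for reasons of efficacy, and an excess of other serious events on caplacizumab can be offset or even reversed in sign.

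At stake is how the most widely read SAE comparison is interpreted. No hypothesis test is involved.

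**Working it through.** **Inputs from the documents.** Phase II results (Protocol 1.2.4) are reported for 75 subjects, and the percentages there imply 36 on caplacizumab (29 is 80.6%) and 39 on placebo (18 is 46.2%).
- Exacerbation during treatment: placebo 11/39 = 28.2%, caplacizumab 3/36 = 8.3%.
- Exacerbation and/or relapse including 1-month follow-up: placebo 11/39 = 28.2%, caplacizumab 10/36 = 27.8%.
- Planning rates for key secondary endpoint 1 (SAP 3.2): 30% placebo, 10% caplacizumab, 132 subjects randomized 1:1.

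**Plan's own figure.** The plan gives no number for the serious-TEAE row. The related figure, about 83% power for key secondary endpoint 1, reproduces. With 66 per arm and pooled variance under the null, (0.20 − 1.96 × √(2 × 0.2 × 0.8/66)) / √((0.3 × 0.7 + 0.1 × 0.9)/66) = 0.942, and Φ(0.942) = 82.7%. Those rates cover the whole composite, so they are not recurrence rates and serve below only as a cross-check.

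**Assumptions.** The documents give no rate for SAEs other than recurrence, so the placebo rate s_p is varied from 10% to 40%. Recurrence and other SAEs are taken as independent within arm.

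**Formula.** With recurrence risk r and other-SAE risk s, P(any SAE) = 1 − (1 − r)(1 − s). Both arms show the same percentage when s_c = 1 − (1 − r_p)(1 − s_p)/(1 − r_c).

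**On-treatment phase II rates.** (1 − 0.2821)/(1 − 0.0833) = 0.7832, so s_c = 1 − 0.7832 × (1 − s_p).

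| Other SAE, placebo | Other SAE, caplacizumab | Any SAE, both arms | Excess not shown |
|---|---|---|---|
| 10% | 29.5% | 35.4% | 19.5 points |
| 20% | 37.3% | 42.6% | 17.3 points |
| 30% | 45.2% | 49.7% | 15.2 points |
| 40% | 53.0% | 56.9% | 13.0 points |

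If no subject has both kinds of event, the excess not shown is 28.2 − 8.3 = 19.9 points throughout. Positive correlation would let the row show more of an excess. The composite planning rates give 20.0 to 13.3 points over the same range.

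**Sign reversal.** Other SAEs of 10% placebo and 20% caplacizumab appear as 1 − 0.7179 × 0.90 = 35.4% and 1 − 0.9167 × 0.80 = 26.7%. That is about 23 and 18 subjects if all 66 per arm are treated, so placebo looks worse.

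**Phase II rates including follow-up.** (1 − 0.2821)/(1 − 0.2778) = 0.9941. With s_p = 10%, s_c = 10.5%; with s_p = 40%, s_c = 40.4%. The masking is 0.4 to 0.5 points.

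**Where it applies.** An exacerbation follows the stop of daily PE, so the double-blind daily-PE row is essentially free of recurrence, apart from events with incomplete dates that default to that subperiod. The double-blind post-daily-PE and overall treatment periods carry the effect. In follow-up the direction may reverse: Protocol 1.2.4 reports 8 caplacizumab subjects in phase II who relapsed in the first month, 7 of them 4 to 10 days after stopping drug.

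**Not used.** The phase II SAE percentages (57.1% caplacizumab, 51.4% placebo) are left out because the documents do not say whether exacerbations were counted in them.

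**The case against.** The best defence is that most of the separation is already planned. Serious TEAEs are tabulated by preferred term, so recurrence should sit on its own line or lines. Event counts are reported too, so non-recurrence events should be obtainable by subtraction. Bleeding, which Protocol 1.2.5 names as the main safety finding, has its own rows, as do treatment-related serious events, thromboembolism, hypersensitivity and events leading to death. All summaries are split by period, and an SAE listing is planned.

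This stands, and it confines the problem to one subject-level row. It does not fill the gap. A subject can have several terms, so subjects with any non-recurrence SAE cannot be summed from a preferred-term table. Deriving them from the listing would not be pre-specified. The treatment-related rows depend on the investigator's causality judgement and do not replace an all-cause count.

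It is also fair that the size depends on assumed other-SAE rates, that phase II recurrence was balanced once follow-up was included, and that the texts of SAP 6.4 and 7.1.3 are not readable in the public copy. An exploratory version of this analysis cannot be excluded.

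A reader might infer that the DSMB judges SAE imbalance on the same mixed count, since "The objective of the DSMB will be to review unblinded safety data on SAEs with a focus on mortality rate". The documents do not support that. Protocol 3.1.1 also gives the board subject-level details and rests on clinical judgement, and the content of its summaries is set in a charter that is not available here.

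**Conclusion.** The point holds for the headline row of Table 14.3.1.1. In the double-blind post-daily-PE and overall treatment periods, equal any-SAE percentages are compatible with an excess of other SAEs on caplacizumab of 13 to 20 points. This rests on phase II on-treatment exacerbation rates, independence, and a placebo other-SAE rate of 10% to 40% that the documents do not give. Where recurrence is balanced, as in phase II with follow-up included, the masking is under 1 point. In follow-up alone the distortion could run against caplacizumab.

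A reader might go further and conclude that the SAE contrast cannot answer the safety question at all. That is not supported, because the period split, the preferred-term tables and the dedicated bleeding and related-event rows remain informative. The summaries are descriptive, so no test, alpha or power changes. This is an inexpensive improvement to a descriptive comparison.

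**What to change.** Leave SAE reporting and the all-SAE row as they are. In Table 14.3.1.1, pre-specify one further row for each analysis period: *at least one serious TEAE other than TTP exacerbation or relapse*, with the number and percentage of subjects and the rate per 100 patient-months. Use it alongside the all-SAE row for any between-arm statement about SAEs. The rate is needed as well as the percentage because data in the randomized-arm columns stop at the switch to open-label drug (SAP 4.3.6), so an arm with more recurrences is observed for less time.

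The cost is one derived flag, set from the recurrences already identified for the key secondary endpoints, and one table row. No new data are needed. The change is neutral to the drug, since it removes the distortion in whichever direction it runs.

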7.2 Laboratory Evaluations

7.2.1 *Available data*

The following parameters will be available:

- **Biochemistry:** sodium, potassium, chloride, urea (BUN), glucose, total bilirubin, alkaline phosphatase, AST, ALT, haptoglobin, total protein, albumin, calcium, C-reactive protein (CRP), globulin.
- **Hematology:** hemoglobin, hematocrit, reticulocytes, erythrocytes, leukocytes, partial automated differentiation: neutrophils, lymphocytes, monocytes, eosinophils, basophils, mean corpuscular volume (MCV), mean corpuscular hemoglobin (MCH), mean corpuscular hemoglobin concentration (MCHC).
- **Coagulation:** activated partial prothrombin time.

7.2.2 *Laboratory units*

The statistical analysis will only present results in Standard International (SI) units. Other units will not be presented.

In the tables, the number of significant digits of the original values will be used to determine the number of decimals that will be printed.

7.2.3 Abnormalities

All values will be compared to their matching normal ranges. The classification available in the standard data tabulation method (SDTM) dataset will not be used for the statistical analysis. The classification will be re-calculated in the analysis data model (ADaM) dataset by using the values and normal ranges in SI units.

Values will be scored as abnormally low (L), normal (N) or abnormally high (H). A value is classified as abnormally low when the value < lower limit of the normal range. A value is classified as abnormally high when the value > upper limit of the normal range. Tests without normal ranges will not be scored. An original value like “ $<X$ ” where X equals the lower limit of the normal range will be classified as abnormally low (L). An original value like “ $>X$ ” where X equals the upper limit of the normal range will be classified as abnormally high (H).

7.2.4 Worst-case abnormality

The worst-case abnormality is derived for each parameter separately.

All non-missing post-baseline values (including unscheduled measurements and follow-up measurements) will be used to derive the following worst-case:

- H = abnormally high: at least one post-dose measurement is above the normal range, and there are no values below the normal range.
- L = abnormally low: at least one post-dose measurement is below the normal range, and there are no values above the normal range.
- H+L = abnormally high and low: at least one post-dose measurement is above the normal range, and at least one other post-dose measurement is below the normal range.
- N = normal: all post-dose measurements are within normal limits

7.2.5 Analysis

For laboratory parameters, descriptive statistics (mean, median, standard error, minimum, and maximum) will be computed on the actual values and the change from baseline for each parameter. All laboratory values will be categorized according to their normal ranges as below, within or above normal. A shift table versus baseline will be created. For selected parameters a shift table will also be created according to an additional categorization:

- AST and ALT: $\leq 1 \times \text{ULN}$ / $>1 \times \text{ULN}$ and $\leq 3 \times \text{ULN}$ / $>3 \times \text{ULN}$ and $\leq 5 \times \text{ULN}$ / $>5 \times \text{ULN}$ and $\leq 20 \times \text{ULN}$ / $>20 \times \text{ULN}$
- Hb: $\leq 8 \text{ g/dL}$ / $>8 \text{ g/dL}$ and $\leq 10 \text{ g/dL}$ / $>10 \text{ g/dL}$
- Leukocytes: $\geq 3000/\text{mm}^3$ / $<3000/\text{mm}^3$ and $\geq 2000/\text{mm}^3$ / $<2000/\text{mm}^3$ and $\geq 1000/\text{mm}^3$ / $<1000/\text{mm}^3$
- Serum creatinine: $\leq 1 \times \text{ULN}$ / $>1 \times \text{ULN}$ and $\leq 1.5 \times \text{ULN}$ / $>1.5 \times \text{ULN}$ and $\leq 3 \times \text{ULN}$ / $>3 \times \text{ULN}$ and $\leq 6 \times \text{ULN}$ / $>6 \times \text{ULN}$

A detailed list of tables, listings and figures can be found in Section [14.7](#), Section [16.8](#) and Section [15.6](#), respectively.

